10.2 Pragmatic interpretation of timepoints

The timepoints above are intended to collect data at the following points in the patients care:

- Baseline Prior to TBM surgery
- 3 weeks Following TBM surgery
- 6 weeks Just prior to starting radiotherapy (if applicable)
- 3 months Just after completing radiotherapy (if applicable)
- 6 months -
- 12 months -

11 Data management

The study will require a database to store pseudonymised data. Patient data will be collected on a paper case report form (CRF) at each site. The CRF will contain no patient identifiable data and will be pseudonymised with a study ID. The CRFs will be sent to the MOSES team at RMH. This will be entered onto an excel spreadsheet held on an NHS trust computer at the sponsoring organisation, the Royal Marsden Hospital NHS Foundation Trust.

All patient identifiable data will remain at the local site subject to normal data governance practices. None will be sent to or handled by the project management team, except for those consenting to the qualitative study who agree to share their name and contact details on the main study ICF.

12 Statistics and data analysis

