12.2 Study endpoints

For the Primary objective:

- Identification of cancer in the tonsillectomy or TBM specimen on histology.

For the Secondary objectives:

- To compare the pick-up rate of primary cancers in TBM specimens between surgical methods (robotic vs laser vs endoscopic).
 - Identification of cancer in the tonsillectomy or TBM specimen on histology.
 - We anticipate no significant disparity in pick up rate between methods with the limited number of cases in this study.
- To prospectively evaluate swallowing function and pain scores after TBM.
 - We anticipate no significant change in means from pain and MDADI scores between 0 and 6 week questionnaires. Results at 3 weeks are anticipated to be different as still recovering from surgery. Results up to 60 months will evaluate effects of any subsequent treatments and future recovery.
- To understand patient views and experiences of undergoing TBM for suspected HNSCCUP.
 - Qualitative thematic analysis therefore no quantitative end point.
- To report time-to-event data for local, regional and distant disease recurrence, and mortality.
 - Primary emergence rate of around 3% per year.
- To assess the molecular makeup of patients with suspected HNSCCUP undergoing TBM.
 - (Exploratory analysis)

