12.4 Analysis methods

Descriptive analysis only is anticipated. The rate of CH and SSS pick up will be reported in the overall specimens and separately in the sub-group of surgical methods with 95% confidence intervals. The pain scores and swallow recovery with MDADI scores will be reported using mean/median and standard deviation or range as appropriate at each time point of 0, 3 weeks, 6 weeks, 3 months, 6 months and 12 months, 24 months, 36 months, 48 months and 60 months. Similarly, score change between time points will be summarized in the same way. The primary and secondary analysis will be done when the complete sample size is recruited and last patient on the study completed all follow-ups.

Molecular data analysis

Detailed description of the molecular analysis methodology is beyond the scope of this protocol.

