12.8 Expected Outcomes of the Study

TBM is a relatively new surgical procedure with little data relating to patients experience and recovery from this operation. The pain and MDADI questions will go some way to showing the acceptability of this procedure to patients. It is expected that by 6 weeks the pain and MDADI scores will have returned to near baseline. Most patients will go on to receive radiotherapy to their pharyngeal mucosa, which is known to worsen swallowing function. This data will go some way to clarifying that any subsequent difficulties may not be attributable to the TBM procedure.

Any increased pick up rate resulting from SSS could lead to wider adoption of this process in the management of HNSCCUP. The size of any primary sites identified through SSS over conventional histology will also be recorded and could influence the size of histological levels employed for future TBM and tonsillectomy specimens in the future management of HNSCCUP.

Data from the patient interviews and thematic analysis should help to guide patient goals for any further research in HNSCCUP. Of particular note will be the patients' wishes regarding timing of the tonsillectomy and TBM procedures, which can occur separately, particularly if initial investigation is performed in a peripheral hospital that does not offer TBM. The potential changes in management from identification of primary sites using SSS, and potential for escalation of treatment through the addition of concomitant chemotherapy will also be novel.

Results from the exploratory molecular analysis are expected to give us greater understanding of the molecular make-up of suspected HNSCCUP. Including, but not limited to, how cancers where the primary is identified differ from those primaries that remain occult, and how the cervical disease differs from primary site tissues in the oropharynx.

Results from this prospective observational study will form the foundation of a potential phase III trial investigating the roles of TBM and SSS in management of suspected HNSCCUP. The precise research question is yet to be established.

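### Section 12.2 wants the pain and MDADI results to evaluate later treatments, but the analysis in 12.4 does not group patients by radiotherapy, so change after 6 weeks cannot be located in either group

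*Protocol*

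**What the plan says.** **Purpose.** Protocol 12.2, under the secondary objective on swallowing and pain, states: "Results up to 60 months will evaluate effects of any subsequent treatments and future recovery". Section 12.8 notes: "Most patients will go on to receive radiotherapy to their pharyngeal mucosa, which is known to worsen swallowing function". It then says of the questionnaire data: "This data will go some way to clarifying that any subsequent difficulties may not be attributable to the TBM procedure".

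**Timing.** Section 10.2 places the 6-week questionnaire immediately before radiotherapy and the 3-month questionnaire immediately after it. Both are qualified as applying only to patients who have radiotherapy, so the protocol expects some who do not.

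**Analysis.** Section 12.4 opens with "Descriptive analysis only is anticipated". Pain and MDADI scores "will be reported using mean/median and standard deviation or range as appropriate at each time point", from baseline to 60 months, and then: "Similarly, score change between time points will be summarized in the same way". The one subgroup named in 12.4 belongs to the pick-up rate, which is reported "separately in the sub-group of surgical methods with 95% confidence intervals". No grouping is named for pain or MDADI.

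**Data.** The CRF contents in 9.4 include the initial treatment plan and the management of further disease. The list refers to the separate CRF document for the full set of fields.

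**The concern.** Evaluating the effect of a later treatment needs, at the least, a view of patients who had it beside patients who did not. The outputs listed in 12.4 give no such view. Followed as written, every summary from 3 to 60 months mixes irradiated and non-irradiated patients.

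At stake is how the late data can be read. If swallowing worsens after 6 weeks, the natural reading is that radiotherapy did it, and 12.8 points that way. The tabulated result would look the same if non-irradiated patients worsened too, which would sit badly with that reading. If only irradiated patients worsen, the all-patient figure understates by how much. A reader of the final report could not tell which had happened.

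**Working it through.** The protocol gives no radiotherapy percentage, no SD and no expected effect size for pain or MDADI, so there is no stated figure to reproduce. All effect sizes, shares and SDs below are assumptions. Worsening is counted as negative.

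**1. What the planned summaries identify.** Let *d* be the mean change from baseline to 6 weeks. Let *r* and *s* be the mean changes from 6 weeks to a later visit in irradiated and non-irradiated patients, and *q* the irradiated share. Section 12.4 yields:

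- baseline to 6 weeks: *d*
- 6 weeks to later: *q·r* + (1 − *q*)·*s*

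The first is clean with respect to radiotherapy, because it ends before radiotherapy starts. The second is one number for two unknowns.

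**2. What the plan can already tell apart.** A TBM effect of -9 that is present by 6 weeks and persists gives *d* = -9 and a later change of 0. A pure radiotherapy effect gives *d* = 0 and a negative later change. The planned change scores separate these two cases.

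**3. What it cannot tell apart.** Take *d* = 0 and an all-patient later change of -9. With *s* = 0, *r* = -9/*q*:

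| Assumed irradiated share *q* | *r* if *s* = 0 | Equally compatible |
|---|---|---|
| 60% | -15.0 | *r* = *s* = -9 |
| 70% | -12.9 | *r* = *s* = -9 |
| 80% | -11.25 | *r* = *s* = -9 |
| 90% | -10.0 | *r* = *s* = -9 |

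The first pattern confines the worsening to irradiated patients; the second does not. The ambiguity exists for any share strictly between 0 and 100%.

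**4. Dilution.** If *s* = 0, the all-patient change is *q·r*. Over assumed shares of 60-90% and assumed irradiated changes of -10 to -20 points, it runs from 0.6 × (-10) = -6 to 0.9 × (-20) = -18.

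**5. Precision of a split.** With the planned 100 patients, full response and an assumed SD of change of 15, the 95% half-width within a group is *t* × 15/√*n*. For the difference between groups, the normal approximation is 1.96 × 15 × √(1/*n*₁ + 1/*n*₀).

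| Irradiated *n*₁ | Non-irradiated *n*₀ | Half-width, non-irradiated | Half-width, difference |
|---|---|---|---|
| 90 | 10 | 2.262 × 15/√10 = 10.7 | 9.8 |
| 75 | 25 | 2.064 × 15/√25 = 6.2 | 6.8 |
| 60 | 40 | 2.023 × 15/√40 = 4.8 | 6.0 |

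These are best cases. Any non-response widens them, and the schedule in 10.1 limits questionnaires after 12 months to patients on the later consent forms.

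**The case against.** **The split may be in an analysis plan that is not shown.** Section 12.4 never says that only all-patient figures will be produced; mixing the groups is inferred from the absence of a grouping. That is fair. The point does not rest on missing detail, though. The protocol gives these data a purpose in 12.2, and its own analysis section, which does name a subgroup where it wants one, lists outputs that do not serve that purpose.

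**The design already addresses TBM.** The 6-week visit precedes radiotherapy, change scores are planned, and a return to near baseline by 6 weeks would be real evidence about the early effect of the operation. This stands. A reader might infer that the late data say nothing about attribution, or that an all-patient decline cannot be told from a general TBM effect. The documents do not support that: step 2 shows that an effect present by 6 weeks would appear in the planned change from baseline. The ambiguity is confined to change that first appears after 6 weeks.

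**Section 12.8 is hedged.** A reader might take the protocol to promise that TBM will be cleared of later swallowing problems. It claims only to go part of the way, so the criticism of 12.8 is that its support is weaker than it need be. The statement in 12.2 carries no such hedge.

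**A split would not settle causation.** Radiotherapy is not randomised, so the groups differ by indication, and the non-irradiated group may be small. Both stand and limit what the fix can deliver. They are not reasons to leave the groups mixed.

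**Treatment received may not be on the CRF.** The protocol lists only the treatment plan and the management of further disease. In 10.1, CRF pages 3 to 5 fall at 3 weeks, before radiotherapy, and page 6 at 12 months. The sponsor has to confirm which field can be used.

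**Conclusion.** The point holds in a limited form. The summaries and change scores in 12.4 do not deliver the evaluation of later treatments that 12.2 states, because they cannot show whether change after 6 weeks arises in irradiated patients, non-irradiated patients or both. The baseline to 6-week comparison is unaffected and remains useful evidence on the early effect of TBM.

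The ambiguity needs only that some, but not all, patients are irradiated, which 10.2 and 12.8 imply. Its size in MDADI points depends on the share irradiated and the true changes, neither of which the protocol gives; the figures above are illustrations. A descriptive split would show where the change occurs, with limited precision and without proof of cause. This is a cheap improvement to a secondary, descriptive endpoint and does not touch the primary objective.

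**What to change.** Add to 12.4, for visits from 3 months on:

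- Pain and MDADI scores, and each patient's change from their own 6-week score, reported by radiotherapy status (any versus none) with 95% confidence intervals. Show chemoradiotherapy separately only if numbers allow.
- The all-patient summary, kept alongside.
- The grouping variable: treatment received if the CRF captures it, otherwise the recorded initial treatment plan. The sponsor should confirm which is available and state it.
- A statement that the comparison is descriptive and confounded by indication.
- A statement that any comment on attribution, as in 12.8, rests on the baseline to 6-week change together with the split table.

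The cost is a few more table rows and wide intervals in the non-irradiated group, as worked out above. No new questionnaire or visit is needed, although a CRF field may be if treatment received is not recorded. Under 12.4 the analysis follows the last patient's final follow-up, which 12.3 projects for October 2028, so on that timetable the text can be settled beforehand. If the split is not wanted, 12.2 should be softened to say that the later results describe the course of symptoms in the whole cohort.

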12.5 Safety Considerations

There are no immediate safety implications anticipated due to the observational and non-interventional nature of the study.

There is potential for primary cancers to be identified in some tissue specimens where it had been missed at the local site when undergoing conventional histology. These updated results from the pseudonymised specimens will not be available in a timeframe that could influence patient treatment.

12.6 Follow-Up

The final patient questionnaires are completed at 60 months post-operatively. Outcome data is derived from the tissue specimens. As above, results from SSS of the tissue specimens will not be fed back to the individual MDT as it will have no potential to influence management which will already have been enacted.

12.7 Quality Assurance

The core MOSES team handling the pseudonymised data have all undergone GCP training with valid contemporary certification.

12.8 Expected Outcomes of the Study

TBM is a relatively new surgical procedure with little data relating to patients experience and recovery from this operation. The pain and MDADI questions will go some way to showing the acceptability of this procedure to patients. It is expected that by 6 weeks the pain and MDADI scores will have returned to near baseline. Most patients will go on to receive radiotherapy to their pharyngeal mucosa, which is known to worsen swallowing function. This data will go some way to clarifying that any subsequent difficulties may not be attributable to the TBM procedure.

Any increased pick up rate resulting from SSS could lead to wider adoption of this process in the management of HNSCCUP. The size of any primary sites identified through SSS over conventional histology will also be recorded and could influence the size of histological levels employed for future TBM and tonsillectomy specimens in the future management of HNSCCUP.

Data from the patient interviews and thematic analysis should help to guide patient goals for any further research in HNSCCUP. Of particular note will be the patients' wishes regarding timing of the tonsillectomy and TBM procedures, which can occur separately, particularly if initial investigation is performed in a peripheral hospital that does not offer TBM. The potential changes in management from identification of primary sites using SSS, and potential for escalation of treatment through the addition of concomitant chemotherapy will also be novel.

Results from the exploratory molecular analysis are expected to give us greater understanding of the molecular make-up of suspected HNSCCUP. Including, but not limited to, how cancers where the primary is identified differ from those primaries that remain occult, and how the cervical disease differs from primary site tissues in the oropharynx.

Results from this prospective observational study will form the foundation of a potential phase III trial investigating the roles of TBM and SSS in management of suspected HNSCCUP. The precise research question is yet to be established.

13.1 Slow recruitment of TBM centres

Early contact with the TBM centres across the UK should improve timely recruitment.

Having undergone SSS, the tissue specimens may have new or additional carcinomas identified. This information will not be available to the treating MDT in a timeframe that could influence patient care. Their treatment plans will have been enacted. The results of the pathological processing will not be fed back to the contributing centres but will only be held in a pseudonymised central MOSES database.

Patients will be asked to complete pain score questionnaires and swallowing function questionnaires. Many centres collect swallow function scores for head and neck cancer patients routinely. These questionnaires will be an additional burden to these patients. However, it is also acknowledged that by asking for these data it may prompt closer attention and better care for these patients.

Patients approached to take part in one-to-one interviews have potential to discuss their perceptions regarding their cancer and cancer management. This could be potentially distressing for some patients. They will be provided with appropriate contact information for Clinical Nurse Specialists throughout the process. They are also eligible to withdraw from the process at any stage without any impact on their care. It is likely that the majority of the patients will have completed their treatment and be in surveillance by the time they are approached to be involved in the interviews.

16 Informed consent process

16.1 Informed Consent Forms

Please see appendix for PISs and ICFs.

Consent for the qualitative interviews is distinct from consent to the main study.

See 'consent' in Section 'Study procedures and methodology' for further information on the consent process.

17 Budget

17.1 Approved funding

This study has been funded by a grant from Oracle Cancer Trust. The following is a summary of the costings for the grant application that were revised and approved on 3rd December 2018:

	Item	Total	Comment
TOTAL COST OF PROJECT	Pathological processing	£ 30,937.50	(£475.96/case)
	Clinical research fellow	£ 50,538.09	Total for 2 yrs
	MD registration fees (ICR)	£ 9,220.00	(£4,610 /yr)
	Qualitative Research Methods Course	£ 1,525.00	https://bit.ly/2DXIbxY
	Supervising PI ([name])	£ 11,567.00	(2hrs/wk)
	[name] (pathology lead)	£ 9,203.80	(2hrs/wk)
	Consensus meeting	£ 5,000.00	
ORACLE GRANT REQUESTED	TOTAL	£ 117,991.39	
	Per Annum	£ 58,995.70	over 2 yrs

This study received a further grant from the Biomedical Research Centre TPT Pump Priming fund. This award of £20,000 will cover Human Tissue Bank costs at RMH and the receipt and transfer of tissue from the contributing units to the laboratory at the RVI in Newcastle. It will also cover reimbursement of patient travel costs, room hire, basic catering/tea/coffee, interview transcription and a licence for the NVIVO coding analysis software for the qualitative interviews.

Statistics and database costs were expected to be around £10,000. However, these costs are no longer applicable, following the award of the TPT Pump Priming grant above.

17.2 Outstanding funding

An application has been made to the Get A-Head charity for continued funding to cover extended recruitment, follow-up and to obtain tissue samples for the exploratory molecular analysis.

17.3 Other support for the Project

We are grateful for the support from Oracle Cancer Trust, the Royal Marsden Hospital, the Institute for Cancer Research and Newcastle upon Tyne Hospitals NHS Foundation Trust.

The salary for the Clinical Research Fellow has also received contributions from the Royal College of Surgeons of England and ENT UK.

18 Collaboration with other scientists or research institutions

18.1 Curriculum Vitae of investigators

The CV of the Principal investigator will be provided.

